7.3 Initial Management of Experimental Arm Subjects

7.3.1 Anticoagulant Therapy in Experimental Arm Subjects

The physician may use UFH or twice-daily LMWH, per Section 6.1.1, as concomitant therapy during PCDT. To minimize the potential for bleeding, the guidelines below should be followed:

1. If UFH is being used as the primary anticoagulant drug during PCDT:

Before starting PCDT: The UFH dose should be adjusted to therapeutic levels by institutional nomogram. At least one PTT (or anti-Xa activity level on a heparin assay, as noted in Section 6.1.1) must be available pre-procedure to ensure that the UFH level will not be supra-therapeutic at the time of PCDT. If the physician's plan is to use UFH as the primary anticoagulant drug during PCDT and the subject was recently receiving LMWH, the physician should wait until at least 8 hours after the last twice-daily LMWH dose, or 18 hours after the last once-daily LMWH dose, before starting PCDT.

During the on-table portion of the PCDT procedure: The UFH dose should be targeted to a therapeutic PTT level (corresponding to 0.3 – 0.7 IU/ml anti-Xa activity on the site's heparin assay). Subjects may receive supplemental bolus doses of UFH (up to 50 units/kg) during PCDT at physician discretion. However, particular caution should be exercised in giving additional UFH doses to patients who are already therapeutically anticoagulated.

During continuous rt-PA infusion: The UFH dose should be reduced to 6-12 units/kg/hr (maximum allowable dose 1000 units/hr) and the PTT maintained at less than 2 times control (there is no lower limit for PTT), or less than 0.5 IU/ml anti-Xa, for that institution. Infusion of UFH directly into the target limb via the sheath is encouraged to ensure the highest heparin concentration in the leg veins. Blood should be drawn at least every 6-8 hours for measurement of PTT or anti-Xa activity level.

2. If **LMWH** is being used as the primary anticoagulant drug during PCDT:

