Before starting PCDT: One of the twice-daily regimens described in Section 6.1.1 should be used. If the patient is already receiving LMWH, the physician should just continue the injections according to the currently planned schedule. If the physician plans to use LMWH as the primary anticoagulant drug during PCDT and the subject was recently receiving UFH, the physician should wait until at least 3 hours after UFH cessation or until the level is shown to be subtherapeutic by a PTT level < 1.5 times control (or a anti-Xa activity level < 0.3 IU/ml), before starting PCDT. If the patient was
not already receiving LMWH but was receiving UFH, the first LMWH dose may be administered at physician discretion as long as the UFH level is not supratherapeutic as determined by PTT or anti-Xa activity level assay.

During the on-table portion of the PCDT procedure: Subjects may receive supplemental bolus doses of UFH (up to 50 units/kg) during PCDT at physician discretion. However, caution should be exercised as these patients are already therapeutically anticoagulated.

During continuous rt-PA infusion: The twice-daily LMWH doses should be given on schedule. Additional UFH should not be given, except for very low doses that may be present within sheath flush solutions, not to exceed 200 units/hour total to the patient.

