 (1) via injection through the vascular sheath or a multisidehole catheter; (2) in Technique A patients only, via the Trellis as described in Appendix 4, Steps 4-8; or (3) in Technique B patients only, via the Angiojet (PowerPulse or Rapid Lysis method) as described in Appendix 5, Step 4.
- 3. Perform a repeat venogram. If significant residual obstructing thrombus is present, position a multisidehole infusion catheter within the thrombus and perform Infusion CDT (rt-PA at 0.01 mg/kg/hr, maximum dose 1.0 mg/hr) as outlined in **Appendix 6**. (For Technique C subjects, this will simply represent a continuation of the initial rt-PA infusion.) The rt-PA infusion should continue until near-complete (> 90%) thrombolysis is observed, clinically-overt bleeding becomes evident, or until a maximum of 24 hours (for Technique A or Technique B) or 30 hours total (for Technique C) of rt-PA infusion has occurred.
- 4. The steps in Section 7.3.5 may be repeated as needed, but the above limits on rt-PA dose, infusion duration, device activation time, and AngioJet infusate volume must be followed.

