Appendix 6: Protocol for Infusion-First PCDT (Technique C)

- 1. Review the initial venogram and estimate the length of the clotted venous segment. Advance a multisidehole catheter into position with its sideholes spanning the thrombus.
- 2. Obtain the following rt-PA solution from the pharmacy: 10mg rt-PA in 10 ml Sterile Water for Injection, USP, diluted to a total volume of 1000 ml in 0.9% normal saline (rt-PA concentration 0.01 mg/ml). Infuse through the multisidehole catheter at a rate of 50-100 ml/hr (corresponding to 0.01 mg/kg/hr, with maximum allowable dose 1.0 mg/hr). For patients in whom fluid volume is of concern or in whom an ultrasound infusion catheter is selected, the physician may concentrate the rt-PA solution to 0.02 mg/ml 0.04 mg/ml (10mg rt-PA in 250-500 ml total volume, infused at 12.5 50 ml/hr). If more than one venous access site is used, the rt-PA dose may be split per physician discretion. The physician may also utilize the vascular sheath (with or without added sideholes) to infuse part of the rt-PA. All infusion catheters should be used per their Instructions for Use (package insert).
- 3. During infusion CDT, the patient should be placed at bedrest and the affected leg should be elevated. Mechanical compression adjuncts may be used per the physician's standard practice. If UFH is used, it should be infused at subtherapeutic levels (6-12 units/kg/hr, maximum allowable dose 1000 units/hr) through the vascular sheath (preferably) or through a peripheral IV (if the sheath is being used to infuse rt-PA), to a target PTT of less than 2 times control. The patient should be monitored in an ICU or stepdown unit and peripheral blood taken at least every 12 hours for hemoglobin, partial thromboplastin time (PTT), and platelet count. A fibrinogen level may be obtained if this is the physician's standard practice.
- The rt-PA infusion may be halted temporarily or permanently at physician discretion if there is evidence of bleeding (see Section 7.3.4), the PTT > 100 seconds, or the fibrinogen level < 100 mg/dl. When rt-PA is stopped, saline should be infused to maintain catheter patency.
- After 6-24 hours, the patient should return to the procedure suite. At each return visit, follow the procedures described in Section 7.3.5. In particular, the use of rheolytic thrombectomy is encouraged at the first follow-up visit to speed thrombolysis (see Appendix 5, Steps 5-9).

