- 6. Technique C patients may receive no more than 30 hours of rt-PA infusion.

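### For patients on unfractionated heparin during a continuous rt-PA infusion, Section 7.3.1 and Appendix 6 set different minimum intervals for PTT testing

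*Protocol*

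**What the plan says.** Section 7.3.1 sets anticoagulation rules for the experimental arm in two branches. The first applies when UFH "is being used as the primary anticoagulant drug during PCDT". Within it, the paragraph on continuous rt-PA infusion reduces UFH to 6-12 units/kg/hr (maximum 1000 units/hr), keeps the PTT below twice control (or anti-Xa below 0.5 IU/ml), and adds: "Blood should be drawn at least every 6-8 hours for measurement of PTT or anti-Xa activity level". The second branch covers LMWH. Its infusion paragraph says "The twice-daily LMWH doses should be given on schedule" and gives no PTT interval.

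Appendix 6, step 3, covers the same period. It says "If UFH is used, it should be infused at subtherapeutic levels (6-12 units/kg/hr, maximum allowable dose 1000 units/hr", with the same PTT ceiling of twice control. It then requires monitoring in an ICU or stepdown unit, with "peripheral blood taken at least every 12 hours for hemoglobin, partial thromboplastin time (PTT), and platelet count". This sentence does not separate UFH from LMWH patients.

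Appendix 6 is not confined to Technique C. For residual thrombus, Section 7.3.5 tells the physician to "perform Infusion CDT (rt-PA at 0.01 mg/kg/hr, maximum dose 1.0 mg/hr) as outlined in Appendix 6", and that includes patients first treated with Technique A or B.

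**The concern.** The same patients, at the same stage of treatment, are given two different minimum testing frequencies. The longer one stands in the appendix that sites are told to follow when they run the infusion. A site that draws blood every 12 hours has done what Appendix 6 asks and has departed from Section 7.3.1. A monitor classifying deviations under Section 17.3 would have no stated rule for deciding whether that counts.

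The interval matters because PTT is the protocol's check on heparin exposure during infusion. Section 18.5.2 presents the PTT ceiling as a protection against bleeding, and Appendix 6, step 4, lists a PTT above 100 seconds as one ground on which the physician may halt rt-PA. How soon either is noticed depends on when blood is drawn. With 30-60 centers planned, the interval used could vary with the page a site works from.

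**Working it through.** The protocol gives no figure of its own to reproduce, so the check is a comparison of texts followed by a count of draws.

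**Side by side, UFH patients on a continuous rt-PA infusion**

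| Item | Section 7.3.1 | Appendix 6, step 3 |
|---|---|---|
| UFH rate | 6-12 units/kg/hr, maximum 1000 units/hr | same |
| PTT ceiling | below 2 times control | same |
| Test | PTT or anti-Xa | PTT, with hemoglobin and platelets |
| Minimum interval | 6-8 hours | 12 hours |

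The heparin rate and ceiling agree, so both texts address the same situation. Only the interval differs. Naming PTT alone in Appendix 6 is not a further conflict: Section 6.1.1 lets sites that routinely use heparin assays substitute anti-Xa wherever a PTT is required. Hemoglobin and platelets do not conflict either, because Section 7.3.1 sets no interval for them.

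**Largest permitted gap.** On the looser reading of Section 7.3.1 the gap is 8 hours; in Appendix 6 it is 12 hours. The excess is 12 - 8 = 4 hours.

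**Minimum number of draws** = infusion hours / interval, rounded down, counting a draw that falls at the end of the infusion.

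- Technique C, where "Technique C patients may receive no more than 30 hours of rt-PA infusion":
  - Appendix 6: 30/12 = 2.5, so 2
  - Section 7.3.1: 30/8 = 3.75, so 3; 30/6 = 5
- Techniques A and B, 24-hour maximum (Section 7.3.5; Appendices 4 and 5, step 12):
  - Appendix 6: 24/12 = 2
  - Section 7.3.1: 24/8 = 3; 24/6 = 4
- A shorter infusion of 12 hours, as an illustration (Appendix 6, step 5, has patients return after 6-24 hours):
  - Appendix 6: 12/12 = 1
  - Section 7.3.1: 12/8 = 1.5, so 1; 12/6 = 2

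**Cross-references.** Step 11 of Appendix 4 and step 11 of Appendix 5 each refer to Section 7.3.1 for heparin use. Appendix 6 refers to Sections 7.3.4 and 7.3.5 and to Appendix 5, and restates the heparin rules itself without naming Section 7.3.1. No statement of precedence between the sections and the appendices was found.

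**The case against.** The strongest defence is that one rule is general and the other specific. The 12-hour sentence covers every infusion patient, including those on LMWH, and describes a combined blood panel. The 6-8 hour rule adds a requirement for UFH patients. Both are floors, so drawing every 6-8 hours satisfies both. The last point stands, and so does the limit to UFH: Section 7.3.1 gives LMWH patients no PTT interval, so nothing conflicts for them. The defence does not remove the inconsistency, because step 3 of Appendix 6 itself sets out the UFH rules and then names PTT at 12 hours without reserving a shorter interval for UFH.

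A reader might infer that a site using Appendix 6 has no reason to test more often. The protocol does not support that. Section 6.2.3.3 names Section 7 together with Appendix 6 as the step-by-step protocol for Technique C, and Section 6.2.6 refers to Section 7.3.1 for anticoagulation during PCDT. What can be said is that Appendix 6 itself gives no prompt.

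Section 6.1.1 also has each center submit its PTT monitoring and UFH dosing nomogram for committee approval. That is a partial control, but it is described for therapeutic-range dosing and does not settle the interval during infusion at reduced heparin.

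**Conclusion.** The inconsistency holds for UFH patients during continuous rt-PA infusion, whether in Technique C or as clean-up after Techniques A and B. At the stated minimums it amounts to 2 draws against 3 to 5 over 30 hours, or 2 against 3 to 4 over 24 hours. These counts assume the infusion runs to its maximum and the site tests no more often than required; shorter infusions narrow the difference.

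A reader might go further and infer that uneven monitoring distorts the comparison of major bleeding. The document does not show this. The interval does not enter the definition of major bleeding (Section 9.1), its blinded adjudication (Section 9.5) or its analysis (Section 15.3.2); halting rt-PA for a high PTT is discretionary; and the UFH rate is capped in both texts. No size of effect on bleeding can be derived. Sample size, power and the primary analysis are untouched. The point is one of safety monitoring and consistent conduct, worth correcting because the correction is so cheap.

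**What to change.** Reconcile Section 7.3.1 and step 3 of Appendix 6 so that one PTT or anti-Xa interval applies to UFH patients during continuous rt-PA infusion. The choice of interval is a clinical one for the investigators, and this review takes no position on it. Add to Appendix 6 the reference to Section 7.3.1 that Appendices 4 and 5 already carry. The cost is a wording change in two places, with notice to the sites; no data collection, sample size or analysis changes.

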Appendix 7: Justification for Using the Villalta PTS Scale

Evidence of the Reliability of the Villalta PTS Scale

- A. In Villalta's study (98), 100 patients were evaluated 6-36 months after venogram-proven DVT. A physician asked the patient to rate the degree to which his/her leg condition interfered with daily life as none, mild, moderate, or severe. Two other physicians independently evaluated the patient, scored the presence of PTS symptoms and signs, and summed the results into a total "Villalta score". Receiver-operator curve (ROC) analysis was used to select optimal cutoff values for the presence and severity (mild, moderate, severe) of PTS, where the criterion standard was interference with the patient's daily life by the condition. Inter- observer agreement was found to be high by the weighted kappa test for PTS signs (0.77), symptoms (0.80), total score (0.78), and PTS severity category (0.75). Interference with the patient's daily life (i.e. clinically important PTS disease burden) was best predicted by the total Villalta score. The sensitivity and specificity of the chosen threshold Villalta score values in discriminating patients with PTS from those without PTS, and between different severity categories, were high.
- B. In a 50-patient substudy to VETO (multicenter DVT cohort study), inter-observer (physiciannurse) reliability coefficients for all clinical sign scale components were moderate to high (weighted kappas 0.59 - 0.84) and the total Villalta score showed even stronger correlations (Pearson coefficient 0.88, p < 0.0001) (81).

- C. In a 125-patient substudy to REVERSE (multicenter VTE cohort study), the total Villalta score showed excellent inter-observer reliability (Pearson coefficient 0.86 0.91) that exceeded that of the composite clinical sign score (0.70 0.75) and the individual clinical sign scores (152).

Hence, all 3 studies found the Villalta Scale to have excellent inter-observer reliability.

Evidence of the Acceptability of the Villalta PTS Scale to DVT Patients and Physicians

The Villalta PTS Scale has been used to identify cases of incident PTS in proximal DVT patients in cross- sectional (10,153) and cohort studies (1,2,5,12,81,129,154), single-center trials (3,4,155,156), and multicenter trials (109). It is the only PTS measure to be successfully used in a multicenter randomized DVT treatment trial (109). Evidence that the Villalta Scale is considered to be a valid method of measuring PTS by physicians is found in the American College of Chest Physicians' 2008 guidelines' strong recommendation in favor of use of elastic compression stockings in DVT patients, which is based upon proof of PTS prevention in studies using the Villalta PTS Scale (3,4,30).

Version 4.0

Evidence of the Validity of the Villalta PTS Scale: Correlation with Health Impairment (QOL)

The construct validity of Villalta's PTS Scale is supported by the demonstration that the total Villalta scores have significantly correlated with QOL in three independent study populations:

- A. In a small (n=41) study (10) of outpatients with first-episode proximal DVT, the presence of PTS on Villalta's PTS Scale, PTS severity category by total Villalta score, and the total Villalta score as a continuous variable (r = 0.63) all correlated strongly with poorer venous disease-specific QOL (p < 0.001).

- B. In 145 patients enrolled in the ELATE Trial (a multicenter trial comparing two intensities of warfarin for proximal DVT), the presence of PTS on Villalta's PTS Scale correlated strongly with poorer venous disease-specific QOL (6.9 points on VEINES-QOL, p < 0.0001) and physical generic QOL (7.4 points on SF-36 Physical Component score, p = 0.0002) (109).

- C. In 359 DVT patients in the VETO Study, the presence of PTS on Villalta's PTS scale independently predicted worsened disease-specific QOL (p < 0.001) and, to a lesser degree, generic QOL (p = 0.04) (12). Evidence of discriminant validity is seen in the fact that the total Villalta score did not correlate with sex, a variable not expected to relate to PTS. In addition, the presence of PTS on Villalta's Scale was shown to be a better predictor of clinically important PTS than imaging criteria such as the presence of valvular reflux on Duplex ultrasound (96). Overall, the strong, graded correlations between the total Villalta scores and venous disease-specific QOL in populations of DVT patients indicate that Villalta's PTS Scale measures a physical condition of major health important PTS).

Evidence of the Validity of the Villalta PTS Scale: Correlations with Venous Disease Indicators

Further evidence that Villalta's PTS Scale is a valid measure of PTS is derived from its **associations with known anatomic/physiologic findings of venous disease**: 1) Abnormal Venograms: In 100 patients with lower extremity symptoms who had undergone venography for suspected DVT > 3 months earlier, Villalta's PTS Scale successfully distinguished patients who did have DVT (positive venograms) from those who did not (negative venograms) (153); 2) Venous Ultrasound Abnormalities: In proximal DVT patients, the presence of PTS on Villalta's PTS Scale was associated with a higher likelihood of Duplex ultrasound venous abnormalities at 6 months (p < 0.001) (26); 3) Elevated Ambulatory Venous Pressures (AVP): In 124 DVT patients, mean AVP increased in graded fashion with increasing PTS severity category on Villalta's PTS Scale (29 mmHg for no PTS, 41 mmHg for mild/moderate PTS, 66 mmHg for severe PTS, p < .001) (157).

Evidence of the Responsiveness of the Villalta PTS Scale to Clinical Change

Patients who reported improvement in generic and venous disease-specific QOL over 4 monthperiod after a DVT episode showed significant reductions in Villalta score during that time (p < 0.001)(12). Hence, based upon the overall weight of evidence, the Villalta PTS Scale is an excellent method to establish the presence of clinically important PTS (1-6,12,26,81,96,98,109, 111,129,152-159).

Appendix 8: Villalta Questionnaire

Assessment of Symptoms of PTS (Villalta)

Patient ID: XXX

Date of assessment: dd/mmm/yyyy

SYMPTOMS (complete for both legs):

Please ask the patient to complete the questions on this page. The nurse or physician performing the assessment of clinical signs of PTS must be blind to these responses.

Q.1 In general, how would you rate the following SYMPTOMS in your **RIGHT** leg? (*please check one response for each symptom*)

	No or Minimal	Mild	Moderate	Severe	
Cramps					
Itching					
Pins and needles					LEG
Leg heaviness					
Pain					

Q.2 In general, how would you rate the following SYMPTOMS in your **LEFT** leg? (*please check one response for each symptom*)

	No or Minimal	Mild	Moderate	Severe
Cramps				
Itching				
Pins and needles				LEFT LEG
Leg heaviness				
Pain				

Appendix 8: Villalta Questionnaire (cont'd)

Assessment of Clinical Signs of PTS (Villalta)

Patient ID: XXXX Date of Assessment: dd/mmm/yyyy Time of Assessment: hh:mm AM PM

SIGNS (complete for both legs):

This form is to be completed by the nurse or physician performing assessment of PTS. Nurse or physician must be blind to responses to previous Symptoms questions.

Q.1 Rate the following SIGNS on the **RIGHT** leg *(please check one response for each sign)*

	No or Minimal	Mild	Moderate	Severe	
Pretibial edema					
Skin induration					
Hyperpigmentation					3
Venous ectasia					
Redness					
Pain during calf compression					
Is an ulcer present? No	Yes				
Circumference 10 cm below ti	bial tuberosity	cm			

Q.2 Rate the following SIGNS on the LEFT leg (please check one response for each sign)

	No or Minimal	Mild	Moderate	Severe
Pretibial edema				
Skin induration				
Hyperpigmentation				LEFT LEG
Venous ectasia				
Redness				
Pain during calf compression				
Is an ulcer present? No	Yes			
Circumference 10 cm below t	tibial tuberosity	cm		

Appendix 9: Revised CEAP Classification of Chronic Venous Disease

- **C** Clinical signs (grade 0-6) supplemented by A for asymptomatic and S for symptomatic presentation
- **E** Etiologic classification (Congenital, Primary, Secondary)
- A Anatomic distribution (Superficial, Deep, or Perforator, alone or in combination)
- **P** Pathophysiologic dysfunction (Reflux or Obstruction, alone or in combination)

C (Clinical) Classification

Class 0 No visible or palpable signs of venous diseas	e
-------------------------------------------------------	---

- Class 1 Telangiectasies or reticular veins
- Class 2 Varicose veins
- Class 3 Edema
- Class 4a Skin changes including pigmentation or venous eczema
- Class 4b Skin changes including lipodermatosclerosis
- Class 5 Healed venous ulceration
- Class 6 Active venous ulceration

E (Etiological) Classification

Ec (Congenital)	The etiology of the chronic venous disease has been present since birth
E _P (Primary)	Idiopathic chronic venous disease
Es (Secondary)	Chronic venous disease with known etiology (e.g. post-thrombotic)
En	No venous cause identified

A (Anatomical)	Classification
----------------	----------------

Superficial veins (A_S) Deep veins (A_D) Perforating veins (A_P) No venous location identified (An) **P** (Pathophysiological) Classification

Reflux (P_R) Obstruction (P_O) Both (P_{RO}) No venous pathophysiology seen (P_N)

Example:

A patient with healed ulcerations known to be related to post-thrombotic syndrome, with documented reflux and obstruction, would be classified as $C_5 E_S A_D P_{RO}$.

Attribute	Absent = 0	$\mathbf{Mild} = 1$	Moderate = 2	Severe = 3
Pain or other discomfort (i.e. aching, heaviness, fatigue, soreness, burning)	None	Occasional pain or discomfort (i.e. not restricting regular daily activity)	Daily pain or discomfort (i.e. interfering with but not preventing regular daily activities)	Daily pain or discomfort (limits most regular daily activities)
Varicose veins Must be $\geq 3 \text{ mm}$ to qualify	None	Few, scattered: (i.e. isolated branch VVs or clusters), includes corona phlebectatica	Multiple: confined to calf or thigh	Multiple: involves calf and thigh
Venous edema Presumes venous origin (i.e. not brawny, not pitting or spongy edema and relieved by elevation)	None	Limited to foot and ankle area	Extends above ankle but below knee	Extends to knee or above
Skin pigmentation Presumes venous origin Does not include focal pigmentation over varicose veins or pigmentation due to other chronic diseases (i.e. vasculitis purpura)	None or focal	Limited to perimalleolar area	Diffuse over lower third of calf	Wider distribution above lower third of calf
Inflammation More than just recent pigmentation (i.e. erythema, cellulites, eczema, dermatitis)	None	Limited to perimalleolar area	Diffuse over lower third of calf	Wider distribution above lower third of calf
Induration Presumes venous origin of secondary skin and subcutaneous changes (i.e. chronic edema with fibrosis, hypodermitis)	None	Limited to perimalleolar area	Diffuse over lower third of calf	Wider distribution above lower third of calf
Number of active ulcers	0	1	2	≥3
Active ulcers: duration (longest active)	None	< 3 months	> 3 mo, < 1 year	Not healed for >1 year
Active ulcers: size (largest active)	N/A	< 2 cm diameter	2-6 cm diameter	> 6 cm diameter

